CDC: United States Centers for Disease Control and Prevention

CFR: Code of Federal Regulations

CLIA: Clinical Laboratory Improvement Amendment of 1988

COI: Conflict of Interest

COVID-19: Coronavirus Disease from SARS-CoV2

CRF: Case Report Form

DMC: Data Management Center

DSMB: Data and Safety Monitoring Board

EUA: Emergency Use Authorization

FDA: Food and Drug Administration

GCP: Good Clinical Practice

HBV: Hepatitis B virus

HCIP: Human Coronavirus Immune Plasma

HCV: Hepatitis C virus

HIV: Human immunodeficiency virus

HTLV: Human T-cell lymphotropic virus

IB: Investigator's Brochure

ICF: Informed Consent (Informed Consent Form)

ICH: International Conference on Harmonization

ICU: Intensive Care Unit

IEC : Independent ethics committee

IND: Investigational New Drug Application

IRB: Institutional review board

ISBT: International Society of Blood Transfusion

ISM: Independent Safety Monitor

IWRS : Interactive web response system

MERS: Middle East Respiratory Syndrome

OP: Oropharyngeal

RT-PCR: Reverse Transcriptase Polymerase chain reaction

PK: Pharmacokinetic

PPE: Personal Protective Equipment

SAE: Serious adverse event

SARS: Severe Acute Respiratory Syndrome

SARS-CoV-2: Severe Acute Respiratory Syndrome Coronavirus 2

TACO: Transfusion-associated circulatory overload

T. cruzi: *Trypanosoma cruzi*

TRALI: Transfusion-related acute lung injury

UP: Unanticipated Problem

UPnonAE: Unanticipated Problem that is not an Adverse Event

ZIKV: Zika virus

PROTOCOL SUMMARY

Phase II Randomized Study of Convalescent Plasma from Recovered COVID-19 Donors Collected by Plasmapheresis as Treatment for Subjects with Early COVID-19 Infection

Background

SARS-CoV-2

The novel coronavirus, SARS-CoV-2, is currently causing a worldwide pandemic with over 700,000 cases as of March 29th, 2020. There is currently no therapy for SARS-CoV-2, and the need for therapeutic options is urgent. The virus appears to cause multiorgan failure through several mechanisms, including a severe inflammatory response leading to acute respiratory distress syndrome.¹

Convalescent plasma for novel viruses

Passive antibody therapy has been used for prior virus epidemics.²⁻⁶ Reports from outbreaks of severe acute respiratory syndrome (SARS) from coronavirus (SARS-CoV-1) showed that convalescent plasma from recovered patients contains neutralizing antibodies.⁷ In the 2013 Ebola epidemic, there was a significant increase in survival (72% vs 56%) for patients receiving convalescent whole blood compared to those who did not.⁸ The proposed mechanism of action by which passive antibody therapy works, is thought to be viral neutralization but may also include antibody-dependent cellular cytotoxicity.

Convalescent plasma in hospitalized patients

We are currently accruing patients on study under IND 19824 of hospitalized patients with COVID-19 infections. With 39/55 patients accrued on this study, we have found that most patients (87%) are showing anti-SARS-CoV2 titer >1:100 by the time of plasma request as very few patients are hospitalized during their first week of symptoms. Conceptually, the use of convalescent plasma is to prevent further viral invasion pending adaptive immunity. Early viral neutralization may prevent the ensuing inflammatory and coagulation cascade.

The purpose of this trial is to intervene in the early phase of viral infection to prevent hospitalization and mortality in the high-risk population.

Study Objectives

Primary Objectives

To compare the hospitalization rate of patients with early COVID-19 infection at high-risk of admission with or without convalescent plasma infusion.

Secondary objectives

- Time to symptoms resolution
- Overall survival
- Rate of virologic clearance by nasopharyngeal swab at 2 and 4 weeks.
- Evaluation of donor parameters including nasopharyngeal swab positivity and titers levels

- Evaluation of the impact of donor titers level on efficacy
- Patients' anti-SARS-CoV2 titer assessment pre-infusion for the Treatment group, +2 weeks (+/- 3 days), +4 weeks (+/- 3 days) and +2 months (+/- 5 days). Randomization day will be designated at day 0.

Exploratory Objectives

These are to be performed at Hackensack Meridian Health Center for Discovery and Innovation

- Plasma product analysis for cytokines, mannose-binding lectin (MBL), procalcitonin (PCT), C-reactive protein (CRP), Human neutrophil lipocalin (HNL), Annexin V, Surfactant protein D (SP-D), as well as microRNAs, quantification of IgG, IgM, IgA. It may not be feasible to draw samples on every plasma bag.
- Patients' cytokines and chemokines levels prior to treatment, +2 and +4 weeks (+/- 3 days) post randomization
- Patient's gut microbiota diversity and composition prior to treatment, +3 day, +7 day, +2 weeks, +4 weeks, and +2 months post randomization

Safety endpoints

- Rates of adverse events associated with convalescent plasma infusion.
- Safety assessment will be performed on infusion day for the Treatment group (immediately post infusion), and for all patients on randomization day +3 and +7 days (by telephone, closest business day is acceptable), +2 weeks (+/- 3 days), +4 weeks (+/- 3 days).

Inclusion Criteria

Donor (see Appendix A)

- Age 18-60
- A history of a positive nasopharyngeal swab for COVID-19 or a history of positive antibody titer test.
- At least 14 days from resolution of COVID-19-associated symptoms including fevers.
- A negative nasopharyngeal swab (or similar test) for COVID-19
- anti-SARS-CoV2 titers $\geq 1:500$
- Adequate venous access for apheresis
- Meets donor eligibility criteria in accordance to Hackensack University Medical Center (HUMC) Collection Facility at the John Theurer Cancer Center (JTCC) if collecting at the JTCC, and all regulatory agencies as described in SOP 800 01 (Appendix A).
- Required testing of the donor and product must be performed in accordance to FDA regulations (21 CFR 610.40), and the donation must be found suitable (21 CFR 630.30)

Patient

- Patient age ≥ 30 years old, newly diagnosed with a COVID-19 infection with onset of first symptoms ≤ 96 hours.
- And least one other high-risk feature:
 1. Age ≥ 65

2. BMI 30 or above
3. Hypertension, defined as SBP above 140 or DBP above 90, or requiring medication for control.
4. Coronary artery disease (history, not ECG changes only)
5. Congestive heart failure
6. Peripheral vascular disease (includes aortic aneurysm \geq 6 cm)
7. Cerebrovascular disease (history of CVA or TIA)
8. Dementia
9. Chronic pulmonary disease
10. Liver disease (such as portal hypertension, chronic hepatitis)
11. Diabetes (excludes diet-controlled alone)
12. Moderate or severe renal disease defined as having a GFR $<$ 60 mL/min
13. Cancer (exclude if \geq 5 year in remission)
14. AIDS (not just HIV positive)

Patient exclusion criteria

- History of severe transfusion reaction to plasma products
- Need for oxygen supplementation
- Positive test for COVID-19 antibodies
- Chemotherapy-induced neutropenia (ANC $<$ $0.5 \times 10^3/\text{mcL}$)
- Immunosuppressive medications except for prednisone (or steroid equivalent) \geq 10 mg daily.
- Performance status $<$ 50 by KPS
- Pneumonia by radiographic evaluation

Treatment Plan

Plasma collection

Collection of plasma will be performed on eligible and suitable donors meeting regulatory requirements (Appendix A).

SARS-CoV-2 convalescent plasma consisting of 1 unit of approximately 400-500 mL or 2 units of approximately 200 mL will be collected by apheresis from a volunteer donor who recovered from COVID-19 infection and was found to have anti-SARS-CoV2 titers $\geq 1:500$.

Donors may be referred to an outside licensed Blood Center for plasmapheresis to be performed as per the licensed Blood Center SOPs.

Convalescent plasma collected under IND 19824 may be used.

Plasma infusion

Approximately 400-500mL of liquid fresh or fresh frozen plasma will be infused one time.

Statistical Analysis

This is a randomized phase II trial to assess the efficacy and safety of treatment with convalescent plasma infusion (Treatment) versus without convalescent plasma infusion (Control) in patients with early COVID-19 infection at high-risk of admission. Eligible subjects will be stratified randomized by their Charlson Comorbidity Index scoring in a 1:1 ratio to receive either Treatment or Control (8.4). For this trial, we have considered a group sequential design which has more interim analyses and utilized a three-stage O'Brien-Fleming design.²³

The first stage analysis will be after 51 subjects in each arm, that is after a total of 102 subjects. If the Z statistic is greater than or equal to 0.179 (p-value ≥ 0.571), the hypothesis H_0 is accepted and the trial stops, we conclude the Treatment is not worth pursuing; if the Z statistic is less than or equal to -2.849 (p-value ≤ 0.002), the hypothesis H_0 is rejected and early evidence for promising efficacy is established. Otherwise, the trial continues to the next stage.

The second stage analysis will be after 102 subjects in each arm, that is after a total of 204 subjects. If the Z statistic is greater than or equal to -0.944 (p-value ≥ 0.173), the hypothesis H_0 is accepted and the trial stops, we conclude the Treatment is not worth pursuing; and if the Z statistic is less than or equal to -2.015 (p-value ≤ 0.022), the hypothesis H_0 is rejected and early evidence for promising efficacy is established. Otherwise, the trial continues to the final stage.

At the final stage, a total of 306 subjects will be recruit and 153 of them for each arm. The hypothesis H_0 is rejected for efficacy if the Z statistic is less than -1.64504 (p-value < 0.4498). Otherwise, the H_0 is not rejected.

Study site

This is a single institution study conducted at Hackensack University Medical Center (HUMC)/John Theurer Cancer Center at HUMC, Hackensack, NJ. The exploratory laboratory tests will be performed at the Hackensack Meridian Health Center for Discovery and Innovation (CDI).

PROTOCOL

Phase II Randomized Study of Convalescent Plasma from Recovered COVID-19 Donors Collected by Plasmapheresis as Treatment for Subjects with Early COVID-19 Infection

1. Introduction

1.1 General principals of passive antibody therapy

There is currently no proven effective therapy for coronavirus disease (COVID-19) caused by Severe Acute Respiratory Syndrome Coronavirus 2 (SARS-CoV-2). Donor convalescent plasma has been successfully used for treatment of other viral infections, and thus may provide an option for the treatment of COVID-19 and could be rapidly available from people who have recovered from the disease and can donate plasma.

Passive antibody therapy involves the administration of antibodies against an infectious agent to an afflicted individual for the purpose of treating their disease. In contrast, active vaccination requires the induction of an immune response, which takes time to develop and varies depending on the recipient. Some immunocompromised patients fail to achieve an adequate immune response. Thus, passive antibody administration may in some instances represent the only way of providing immediate immunity to susceptible persons, and more predictable immunity in immunocompromised patients. It also offers the potential for immediate benefit in hospitalized and ICU patients who are critically ill.

Passive antibody was first described in the 1890s, and was the only way to treat certain infectious diseases prior to the development of antimicrobial therapy in the 1940s.²⁻⁶ Experience from prior outbreaks with other coronaviruses such as SARS-CoV-1 shows that convalescent plasma contains neutralizing antibodies to the relevant virus.⁷ In the case of SARS-CoV-2, the anticipated mechanism of action by which passive antibody therapy would mediate protection is viral neutralization. However, other mechanisms may be possible, such as antibody-dependent cellular cytotoxicity or phagocytosis. Convalescent serum was also used in the 2013 African Ebola epidemic. A small non-randomized study in Sierra Leone revealed a significant increase in survival for those treated with convalescent whole blood relative to those who received standard treatment.⁸

The only antibody therapy currently available for immediate use in SARS-CoV-2 is found in human convalescent plasma. As more individuals contract COVID-19 and recover, the number of potential donors will continue to increase.

A general principle of passive antibody therapy is that it is more effective when used early in the treatment of disease. Antibody therapy is most effective when administered shortly after the onset of symptoms. The reason for temporal variation in efficacy is not well understood but could reflect that passive antibody works by neutralizing the initial inoculum, which is likely to be much smaller than that of established disease. Another explanation is that antibody works by modifying the inflammatory response, which is also easier during the initial immune response.⁴ As an example, passive antibody therapy for pneumococcal pneumonia was most effective when administered shortly after the onset of symptoms and there was no benefit if antibody administration was delayed past the third day of disease.²

For passive antibody therapy to be effective, enough antibody must be administered. When given to a susceptible person, this antibody will circulate in the blood, reach tissues and provide protection against infection. Depending on the antibody amount and composition, the protection conferred by the transferred immunoglobulin can last from weeks to months. Therefore, the use of a larger amount of plasma collected by apheresis may be preferable to plasma separated from a unit of whole blood.

1.2 Experience with the use of convalescent plasma to treat coronavirus infections

In recent times there have been two other epidemics with coronaviruses that were associated with high mortality, SARS1 in 2003 and MERS in 2012. In both outbreaks, the high mortality and absence of effective therapies led to the use of convalescent plasma. The largest study involved the treatment of 80 patients in Hong Kong with SARS.⁹ Patients treated before day 14 had improved prognosis defined by discharge from hospital before day 22, consistent with the notion that earlier administration is more likely to be effective. In addition, those who were PCR positive and seronegative for coronavirus at the time of therapy had improved outcomes. There is also some anecdotal information on the use of convalescent plasma in seriously ill individuals. Three patients with SARS in Taiwan were treated with 500 ml of fresh convalescent plasma, resulting in a reduction in plasma virus titer and each survived.¹⁰ Three patients with MERS in South Korea were treated with convalescent plasma, but only two of the recipients had neutralizing antibody in their plasma.¹¹ The latter study highlights a challenge in using convalescent plasma, namely, that some who recover from viral disease may not have high titers of neutralizing antibody.¹² Consistent with this point, an analysis of 99 samples of convalescent sera from patients with SARS showed that 87 had neutralizing antibody with a geometric mean titer of 1:61.⁷ This suggests that antibody declines with time or that few patients make high titer responses.

It is also possible that other types of non-neutralizing antibodies are made that contribute to protection and recovery as described for other viral diseases.¹³

Convalescent plasma has been reported in a case series of patients with SARS-CoV-2.²⁰ Patients received transfusion with 400-500 mL of fresh convalescent plasma with a SARS-CoV-2-specific antibody binding titer greater than 1:1000 and a neutralization titer greater than 40 that had been obtained from 5 patients who recovered from COVID-19. Convalescent plasma was administered between 10 and 22 days after admission. All 5 patients were receiving mechanical ventilation at the time of treatment and all had received antiviral agents and methylprednisolone. ARDS resolved in 4 patients at 12 days after transfusion, and 3 patients were weaned from mechanical ventilation within 2 weeks of treatment. Of the 5 patients, 3 have been discharged from the hospital, and 2 are in stable condition at 37 days after transfusion. Since this is the only available data for SARS-CoV2 available, the infusion of a larger volume (400-500mL) of fresh plasma would be supported.

1.3 Overview of safety

Historical and current anecdotal data on use of convalescent plasma suggest that it is safe in coronavirus infection. The theoretical risk involves the phenomenon of antibody-dependent enhancement of infection (ADE). For coronaviruses, several mechanisms for ADE have been described and there is the theoretical concern that antibodies to one type of coronavirus could enhance infection to another viral strain.¹⁴ Since the proposed use of convalescent plasma in the COVID-19 epidemic would rely on preparations with high titers of neutralizing antibody against the specific virus, SARS-CoV-2, ADE may be unlikely. The available evidence from the use of convalescent plasma in patients with SARS1 and MERS,¹⁵ and the case series evidence of its use in patients with COVID-19²⁰ suggests it is safe.

Another theoretical risk is that antibody administration to those exposed to SARS-CoV-2 may avoid disease but modify the immune response such that those individuals mount attenuated immune responses, which would leave them vulnerable to subsequent re-infection. In this regard, passive antibody administration before vaccination with respiratory syncytial virus was reported to attenuate humoral but not cellular immunity.¹⁶ This concern will be investigated as part of this clinical trial by measuring immune responses in those exposed and treated with convalescent plasma to prevent disease. If the concern proved real, these individuals could be vaccinated against COVID-19 when a

vaccine becomes available. The antibodies used in this study will be derived from serum obtained from convalescent patients and will be subjected to testing protocols used by blood banks and transfusion services. However, as is the case with any biological product, there is a very small risk of allergy or anaphylaxis, transfusion related acute lung injury (TRALI), and transfusion associated circulatory overload (TACO) or passive transfer of potential unknown infectious agents. Most adverse effects are mild and transient including headaches, flushing, fever, chills, fatigue, nausea, diarrhea, blood pressure changes and tachycardia. Late adverse events are rare.

1.4 Experience at HUMC/JTCC with convalescent plasma in patients with COVID-19

To date 39 patients with COVID-19 hospitalized at HUMC were treated with convalescent plasma under IND 19824. Our review of these patients showed that the treatment is safe with only 1 patient with a plasma infusion-associated rash. Our experience revealed that most patients admitted for COVID-19 were in the second week of their disease and were experiencing immune mediated hypoxemia. 87% of the treated patients were found to have anti-SARS-CoV2 antibody titers prior to the infusion of plasma. This was unexpected at the time of inception of our protocol under IND 19824. The unmet need appears to be in the week preceding admission where patients have unprotected viral infection and tissue invasion. There is precedent of the introduction of antiviral therapy early in the disease process. The oral neuraminidase inhibitor oseltamivir has shown efficacy in reducing duration of symptoms and complication from influenza in patients with less than 36 hours from symptom onset.²¹ We believe that a similar strategy needs to be implemented for convalescent plasma in COVID-19 patients.

2. Study Objectives

2.1 Primary objectives

To compare the hospital admission rate of patients with early COVID-19 infection at high-risk of admission with or without convalescent plasma infusion.

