7.3 Data Safety Monitoring Board (DSMB)

This study will be approved and monitored by the HackensackUMC DSMB. The DSMB is responsible for the monitoring of investigator initiated research studies to ensure the safety of participants, the integrity of the data, and the appropriate termination of studies in the event that undue risks have been uncovered, or it appears that trials cannot be conducted successfully. The DSMB provides multidisciplinary, independent oversight of research studies conducted by HackensackUMC staff and or affiliates. The DSMB can require protocol modifications related to participant safety and to recommend suspension or termination to the IRB and institutional official of any research protocols that fall within its jurisdiction. The DSMB may request that HackensackUMC's Corporate Compliance Department conduct periodic audits to assure that data are being collected and recorded according to the protocol.

The investigator is required to submit monthly monitoring reports which include current enrollment data, adverse event summary data and any other data requested by the DSMB. The DSMB will meet monthly to review the trial progress, adverse event data, and any relevant information such as significant amendments or reviews from IRB submitted by the principal investigator. If significant concerns are raised by the DSMB, the concerns will be forwarded to the PI as well as recommendations made to the IRB, and Institutional Official. Recommendations may include modifying, suspending, or terminating the protocol.

8. Study Design and Sample Size Considerations

This is a randomized phase II trial to assess the efficacy and safety of treatment with convalescent plasma infusion (Treatment) versus without convalescent plasma infusion (Control) in patients with early COVID-19 infection at high-risk of admission. Eligible subjects will be stratified randomized by their Charlson Comorbidity Index scoring in a 1:1 ratio to receive either Treatment or Control (8.4). For this trial, we have considered a group sequential design which has more interim analyses and utilized a three-stage O'Brien-Fleming design.²³

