8.1 Hypothesis

The primary objective is the hospitalization rate of patients with early COVID-19 infection at high-risk of admission. Suppose the hospitalization rate by 21 days from therapy initiation is 8% for the Treatment group (P_t) and 18% for the Control group (P_c). This phase II design will aim at the following hypothesis:

The design has a type I error rate at 0.05 with statistical power at least 0.80.

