8.2 Study design

This trial will follow a one-sided three-stage O'Brien-Fleming design as follows.²³

The first stage analysis will be after 51 subjects in each arm, that is after a total of 102 subjects. If the Z statistic is greater than or equal to 0.179 (p-value ≥ 0.571), the hypothesis H_0 is accepted and the trial stops, we conclude the Treatment is not worth pursuing; if the Z statistic is less than or equal to -2.849 (p-value ≤ 0.002), the hypothesis H_0 is rejected and early evidence for promising efficacy is established. Otherwise, the trial continues to the next stage.

The second stage analysis will be after 102 subjects in each arm, that is after a total of 204 subjects. If the Z statistic is greater than or equal to -0.944 (p-value ≥ 0.173), the hypothesis H_0 is accepted and the trial stops, we conclude the Treatment is not worth pursuing; and if the Z statistic is less than or equal to -2.015 (p-value ≤ 0.022), the hypothesis H_0 is rejected and early evidence for promising efficacy is established. Otherwise, the trial continues to the final stage.

At the final stage, a total of 306 subjects will be recruit and 153 of them for each arm. The hypothesis H_0 is rejected for efficacy if the Z statistic is less than -1.64504 (p-value < 0.4498). Otherwise, the H_0 is not rejected.

Stage	Cumulative total sample size N	Cumulative sample size for treatment group N(Grp 1)	Cumulative sample size for control group N(Grp 2)	Evidence for undesired rate if Z statistic \geq (Accept H_0 if Z-statistic \geq)	Evidence for desired rate if Z statistic \leq (Reject H_0 if Z-statistic \leq)	Evidence for undesired rate if p-value \geq (Accept H_0 if p-value \geq)	Evidence for desired rate if p-value \leq (Reject H_0 if p-value \leq)
1	102	51	51	0.17929	-2.84929	0.57115	0.00219
2	204	102	102	-0.94399	-2.01475	0.17259	0.02197
3	306	153	153	-1.64504	-1.64504	0.04998	0.04998

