8.3. Analysis Plan

8.3.1 Primary Endpoints

The primary endpoint of the phase II study is the hospitalization rate at 10 days from therapy initiation of patients with early COVID-19 infection at high-risk of admission. The hospitalization rate will be summarized by frequency (%) and compared between the Treatment and Control arms by Mantel-Haenszel test. There will be two interim analyses. Analysis reports will be provided to the DSMB to decide if there is a pronounced treatment effect or futility. A detailed interim analysis plan will be provided before the start of the interim analysis.

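### The primary endpoint is hospital admission alone with no rule for death before admission, so by implication an unadmitted death counts as a non-event

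*Combined protocol and SAP*

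**What the plan says.** Section 2.1 gives the primary objective: "To compare the hospital admission rate of patients with early COVID-19 infection at high-risk of admission with or without convalescent plasma infusion". The Protocol Summary objective is the same in substance. Section 8.3.1 defines the endpoint: "The primary endpoint of the phase II study is the hospitalization rate at 10 days from therapy initiation". It sets the analysis: "The hospitalization rate will be summarized by frequency (%) and compared between the Treatment and Control arms by Mantel-Haenszel test". Section 8.1 plans on hospitalization rates of 8% (Treatment) and 18% (Control), but by 21 days rather than 10.

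None of these places makes death part of the event, counts death before admission as a failure, or treats it as a competing event. The primary endpoint also has no analysis set and no missing-data rule.

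Death is handled elsewhere: overall survival as a secondary endpoint and censoring in time to symptom resolution (both 8.3.3), a safety count (8.3.2), and one of the ways to complete the study (5.4.1). The Background in the Protocol Summary states the purpose of the trial as "to prevent hospitalization and mortality in the high-risk population".

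**The concern.** A patient who dies at home is not hospitalized. In a plain frequency of hospitalizations that patient stays in the denominator and adds nothing to the numerator, so the worst outcome lowers the arm's event rate. Excess unadmitted deaths on Treatment would be hidden from the primary test, and an excess on Control would hide benefit. The same statistic is compared with the efficacy and futility bounds at both interim analyses, so the stopping decisions are exposed too.

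Such deaths are possible in this population. Patients are treated outside hospital. Each has at least one high-risk feature, which may be dementia, heart failure or cancer (3.2). Only a performance status below 50 is excluded (3.3), and proxy consent is allowed (5.2.1).

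**Working it through.** **Inputs.** Rates of 8% and 18% (8.1); "The design has a type I error rate at 0.05 with statistical power at least 0.80" (8.1); "This trial will follow a one-sided three-stage" design with 51, 102 and 153 per arm and the printed Z bounds (8.2); allocation "in a 1:1 ratio to receive either Treatment or Control" (section 8 introduction). Negative Z favours Treatment. The rate of death without admission is not in the documents, so every value used for it below is an assumption.

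**Step 1: reproduce the plan's figure.** With unpooled variance, the expected final Z is

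(0.08 - 0.18) / sqrt((0.08 × 0.92 + 0.18 × 0.82) / 153) = -0.10 / 0.0380 = -2.63.

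Numerical integration over the printed bounds at information 1/3, 2/3 and 1, with binding futility, gives a type I error of 0.050 and power of 0.802 (0.794 with pooled variance). The smallest size per arm reaching 0.80 is 153 (156 pooled). The stated 306 therefore reproduces for admission alone.

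**Step 2: weight of one death.** One unadmitted death moves an arm's rate by 1/51 = 2.0 points at stage 1 and 1/153 = 0.65 points at the final stage. At a pooled rate of 13%, the final bound corresponds to a difference of 1.645 × sqrt(2 × 0.13 × 0.87 / 153) = 0.063, or 6.3 points.

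**Step 3: can it change a decision?** The statistic is the unstratified pooled Z = (x/n - y/n) / sqrt(2p(1 - p)/n), with p = (x + y)/(2n). The counts are illustrative.

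| Stage | Counting | Treatment vs Control | Z | Bound | Decision |
|---|---|---|---|---|---|
| Final, n = 153 | Admission only | 16 vs 26 | -1.66 | -1.645 | Reject |
| Final, n = 153 | Plus 1 Treatment death | 17 vs 26 | -1.48 | -1.645 | Not rejected |
| Stage 1, n = 51 | Admission only | 10 vs 9 | 0.25 | 0.179 | Stop for futility |
| Stage 1, n = 51 | Plus 1 Control death | 10 vs 10 | 0 | 0.179 | Continue |
| Final, n = 153 | Admission only | 12 vs 28 | -2.71 | -1.645 | Reject |
| Final, n = 153 | Plus 5 Treatment deaths | 17 vs 28 | -1.78 | -1.645 | Reject |
| Final, n = 153 | Plus 6 Treatment deaths | 18 vs 28 | -1.60 | -1.645 | Not rejected |

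One death can reverse a close result in either direction. Near the planned effect (12 vs 28) it takes six on Treatment and none on Control: 6/153 = 3.9% of the arm, and half as many as its 12 admissions.

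**Step 4: power of a composite at the same N and bounds.** The assumed unadmitted deaths are added to the 8% and 18% admission rates, using the Step 1 formula and integration (unpooled variance).

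| Unadmitted deaths, Treatment / Control | Composite rates | Expected final Z | Power |
|---|---|---|---|
| 0 / 0 | 8% vs 18% | -2.63 | 0.802 |
| 0.5% / 0.5% | 8.5% vs 18.5% | -2.59 | 0.791 |
| 1% / 1% | 9% vs 19% | -2.55 | 0.780 |
| 2% / 2% | 10% vs 20% | -2.47 | 0.759 |
| 1% / 0 | 9% vs 18% | -2.32 | 0.713 |
| 2% / 0 | 10% vs 18% | -2.03 | 0.613 |
| 0 / 1% | 8% vs 19% | -2.85 | 0.854 |
| 0 / 2% | 8% vs 20% | -3.07 | 0.895 |

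Balanced deaths cost about 1 to 4 points of power. Imbalanced deaths change the answer more, and it is this imbalance that the admission-only endpoint cannot see.

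**The case against.** The strongest reply is that the plan is silent rather than wrong. It states no scoring rule for death, and 8.3.1 promises a detailed interim analysis plan that might supply one. This stands in part: the scoring is implied by the definition and not written out. But nothing in the documents removes such a patient or sets the outcome to missing, so following the text as it stands gives a non-event.

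Second, deaths stay visible. Overall survival is compared by log-rank test, fatal events are serious adverse events (7.2.1), and the DSMB reviews safety monthly (7.3). A reader might infer that the trial ignores death; the documents do not support that. None of these routes, however, enters the primary test or the 8.2 bounds.

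Third, the number of such deaths is probably small. Patients who need oxygen or have radiographic pneumonia are excluded (3.3), symptoms must have begun within 96 hours (3.2), and contacts on days 3 and 7 and at 2 weeks (5.2.3, 5.2.4) give chances to detect deterioration. This stands and limits the point to close or imbalanced results.

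Fourth, a reader might see a contradiction between the stated purpose and the endpoint. The objectives divide that purpose, with admission primary and survival secondary, so this is a mismatch of emphasis and not an internal contradiction.

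**Conclusion.** The point holds as an inexpensive improvement to the endpoint definition. The primary event is admission alone, death before admission has no rule, and by implication an unadmitted death counts as a non-event in the primary test and at every stopping bound.

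Its size cannot be fixed from the documents, because no rate of death without admission is given. On illustrative counts, one such death reverses a result lying at a bound, while six in one arm and none in the other are needed near the planned effect. These Z values are unstratified; a Mantel-Haenszel test stratified by Charlson group could differ slightly.

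A reader might conclude that the sample size is wrong. It is not: 306 reproduces on the plan's own rates. Nor can the documents show that the result will be biased, since that needs an imbalance in deaths that nothing in them predicts.

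**What to change.** - First reconcile the primary window, which is 10 days in 8.3.1 and 21 days in 8.1. It decides which deaths count, and the composite is undefined until it is settled.
- Define the primary event as hospital admission or death from any cause within that window. Keep admission alone as a supporting analysis.
- Change the wording in the Protocol Summary objectives, 2.1, 8.1 and 8.3.1 before the first interim analysis, and carry it into the interim analysis plan.
- Keep N = 306 and the 8.2 bounds. Either state that 8% and 18% are now assumed admission-or-death rates, or restate the power as about 0.79, 0.78 or 0.76 for an assumed 0.5%, 1% or 2% of unadmitted deaths in each arm.

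**Cost.** Wording only, since deaths are already collected. Section 5.4.1 allows for a death whose date cannot be obtained, so one sentence should say how such a death is placed relative to the window. The downsides are that the endpoint becomes a composite and the stated power may be slightly lower.
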